11 ADVERSE EXPERIENCE REPORTING AND DOCUMENTATION

11.1 Adverse Events

An adverse event (AE) is any untoward medical occurrence in a clinical investigation of a patient administered a pharmaceutical product and that does not necessarily have a causal relationship with the treatment. An AE is therefore any unfavorable and unintended sign (including an abnormal laboratory finding), symptom or disease temporally associated with the administration of an investigational product, whether or not related to that investigational product. An unexpected AE is one of a type not identified in nature, severity, or frequency in the current protocol or of greater severity or frequency than expected based on the information in the protocol.

The study team will collect AE information in the headache diary data. Adverse events will be recorded in the patient CRF. Adverse events will be described by severity, outcome, treatment and relation to study drug, or if unrelated, the cause.

AE Severity

The National Cancer Institute's Common Terminology Criteria for Adverse Events (CTCAE) Version 3.0 should be used to assess and grade AE severity, including laboratory abnormalities judged to be clinically significant. The modified criteria can be found in the study manual. If the experience is not covered in the modified criteria, the guidelines shown in

Table 1 below should be used to grade severity. It should be pointed out that the term "severe" is a measure of intensity and that a severe AE is not necessarily serious.

Table 1. AE Severity Grading

Severity (Toxicity Grade)	Description
Mild (1)	Transient or mild discomfort; no limitation in activity; no medical intervention or therapy required. The subject may be aware of the sign or symptom but tolerates it reasonably well.
Moderate (2)	Mild to moderate limitation in activity, no or minimal medical intervention/therapy required.
Severe (3)	Marked limitation in activity, medical intervention/therapy required, hospitalizations possible.
Life-threatening (4)	The subject is at risk of death due to the adverse experience as it occurred. This does not refer to an experience that hypothetically might have caused death if it were more severe.

AE Relationship to Study Drug

The relationship of an AE to the study drug should be assessed using the following the guidelines in Table 2.

Table 2. AE Relationship to Study Drug

Relationship to Drug	Comment
Definitely	Previously known toxicity of agent; or an event that follows a reasonable temporal sequence from administration of the drug; that follows a known or expected response pattern to the suspected drug; that is confirmed by stopping or reducing the dosage of the drug; and that is not explained by any other reasonable hypothesis.
Probably	An event that follows a reasonable temporal sequence from administration of the drug; that follows a known or expected response pattern to the suspected drug; that is confirmed by stopping or reducing the dosage of the drug; and that is unlikely to be explained by the known characteristics of the subject's clinical state or by other interventions.
Possibly	An event that follows a reasonable temporal sequence from administration of the drug; that follows a known or expected response pattern to that suspected drug; but that could readily have been produced by a number of other factors.
Unrelated	An event that can be determined with certainty to have no relationship to the study drug.

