1.1 Overview of Non-Clinical Studies

Melatonin is a well-known and well-established substance, and there are no relevant non-clinical studies or safety concerns pertinent to using this drug for a migraine indication.

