2.1 Risk / Benefit Assessment

2.2 Very low risks to participating in this study, and inconvenience to the participant/family is minimized as most/all study activities can be completed from the participant's home.

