16.2 Institutional Review Boards and Independent Ethics Committees

The protocol and consent form will be reviewed and approved by the UCSF IRB prior to study initiation. Serious adverse experiences regardless of causality will be reported to the IRB in accordance with the standard operating procedures and policies of the IRB, and the Investigator will keep the IRB informed as to the progress of the study. The Investigator will obtain assurance of IRB compliance with regulations.

Any documents that the IRB may need to fulfill its responsibilities (such as protocol, protocol amendments, consent forms, information concerning patient recruitment, payment or compensation procedures, or other pertinent information) will be submitted to the IRB. The IRB's written unconditional approval of the study protocol and the informed consent form will be in the possession of the Investigator before the study is initiated. The IRB's unconditional approval statement will be implemented by the Investigator prior to the shipment of study supplies to the site. This approval must refer to the study by exact protocol title and number and should identify the documents reviewed and the date of review.

Protocol and/or informed consent modifications or changes may not be initiated without prior written IRB approval except when necessary to eliminate immediate hazards to the patients or when the change(s) involves only logistical or administrative aspects of the study. Such modifications will be submitted to the IRB and written verification that the modification was submitted and subsequently approved should be obtained.

The IRB must be informed of revisions to other documents originally submitted for review; serious and/or unexpected adverse experiences occurring during the study in accordance with the standard operating procedures and policies of the IRB; new information that may affect adversely the safety of the patients of the conduct of the study; an annual update and/or request for re-approval; and when the study has been completed.

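### Table 2 leaves a plausibly timed adverse event of a new type without a causality grade, and lets a known reaction be graded Definitely with no test of timing sequence or alternative cause

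*Combined protocol and SAP*

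**What the plan says.** Section 11.1 asks that every adverse event be described by severity, outcome, treatment and relationship to study drug, and that the relationship be assessed with the guidelines in Table 2. The four rows are:

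- *Definitely* opens with two alternatives: "Previously known toxicity of agent; or an event that follows a reasonable temporal sequence from administration of the drug". The timed alternative continues with further conditions: "that follows a known or expected response pattern to the suspected drug; that is confirmed by stopping or reducing the dosage of the drug", and no other reasonable explanation.
- *Probably* requires timing, the same pattern and dechallenge conditions, and that the child's clinical state or other interventions are an unlikely explanation.
- *Possibly* requires timing and that the event "follows a known or expected response pattern to that suspected drug; but that could readily have been produced by a number of other factors".
- *Unrelated* is "An event that can be determined with certainty to have no relationship to the study drug".

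There is no grade for an unlikely or unassessable relationship. Section 14.3 tabulates adverse events by treatment group, with relationship to study drug as one of the items shown. Tolerability is a secondary objective (section 3.2). Under section 2 it decides which dose goes forward if the doses are equally effective.

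**The concern.** A causality scale should give every adverse event one grade, and the grade should rise with the evidence that the drug caused the event. Table 2 appears to fail at both ends.

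At the lower end, each related grade (apart from the known-toxicity route) asks whether the event resembles something already known, and the only other grade demands certainty of no relationship. A reaction not seen before falls between them. This pilot tries melatonin, in a chocolate product that also contains chamomile extract, for acute migraine at ages 3 to 17. A reaction of a new type is something its safety data should be able to record.

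At the upper end, a familiar reaction is graded Definitely because it is familiar, even when its timing is poor or the migraine attack readily explains it.

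The study is open label (section 8.2). Where the criteria give no answer, or too strong a one, an assessor who can know the dose has to improvise. Relationship grades in the two dose groups could then be inconsistent.

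**Working it through.** The plan gives no figure to reproduce. The check treats the rows of Table 2 as logical conditions and enumerates cases.

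**Inputs, all from Table 2**

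- K: previously known toxicity
- T: reasonable temporal sequence
- P: known or expected response pattern
- D: confirmed by stopping or reducing the dose
- A: alternative explanation, at one of three levels (none reasonable, unlikely, readily available)
- U: certainly no relationship

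**Rows as conditions, plain reading**

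- Definitely = K, or (T and P and D and A = none)
- Probably = T and P and D and A = none or unlikely
- Possibly = T and P and A = readily available
- Unrelated = U

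For a fixed type of event there are 2 (T) × 2 (D) × 3 (A) = 12 combinations.

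**Event of a new type, not certainly unrelated (K = no, P = no, U = no).** Every route to Definitely, Probably or Possibly needs K or P, and both are absent. Unrelated needs U, also absent. Result: no grade in 12 of 12 combinations. Of these, 1 × 2 × 3 = 6 have a reasonable temporal sequence, and those are the ones that matter most.

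**Known toxicity (K = yes, P = yes, U = no).** K alone satisfies Definitely, so the result is Definitely in 12 of 12 combinations:

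- 1 × 2 × 3 = 6 have no reasonable temporal sequence.
- 2 × 2 × 1 = 4 have a readily available alternative cause. The 2 of these 4 that are well timed also meet Possibly, so one event satisfies two very different grades.

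**A stricter reading of Definitely.** Suppose the later conditions were meant to bind the known-toxicity alternative too: (K or T) and P and D and A = none. Known toxicity is then Definitely in 2 of 12 combinations, one of them still without a reasonable temporal sequence. The new-type result stays at 12 of 12 without a grade. The first defect therefore does not depend on the reading, while the size of the second does.

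**Does section 11.1 repair the timing elsewhere?** Its general definition of an adverse event already includes temporal association with dosing. That is a condition for being recorded at all. It is looser than the reasonable sequence that the other related grades require, and it says nothing about alternative causes.

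**After the rewording proposed below.** Take an alternative cause that is only readily available as not yet a clear explanation.

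- New type: 6 Possibly (T = yes) + 6 Unrelated (T = no) = 12.
- Known toxicity: 2 Definitely + 1 Probably + 3 Possibly + 6 Unrelated = 12.

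Every combination then has a grade. With each event given the highest grade whose conditions it meets, none has two.

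**The case against.** The strongest reply is that Table 2 is offered as guidelines, not as an algorithm. An experienced investigator would grade a new, well-timed event Possibly and would not call an implausibly timed one Definitely. Relationship is one descriptor among several, both dose groups are graded by the same rules, no text defines tolerability by the relationship grade, and tolerability matters to dose choice only if efficacy is equal. Most of this stands, and it limits the consequence: no distortion of the dose choice is shown. It does not remove the defect, because a grade given by setting the written criterion aside is not one that the tabulation can be said to follow.

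Three stronger readings are tempting, and the documents do not support them.

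- *A missing list of expected reactions causes these defects.* It does not. Table 2 never says that a known pattern must be one named in the protocol. A new type of reaction would have no grade even with a list, and the Definitely problem comes from the word joining its two alternatives.
- *Every adverse event is unexpected.* Section 11.1 says "An unexpected AE is one of a type not identified in nature, severity, or frequency in the current protocol", while sections 1.1 and 2.2 offer only general reassurance ("there are no relevant non-clinical studies or safety concerns pertinent to using this drug for a migraine indication" and "Very low risks to participating in this study"). A reader might conclude that even sleepiness is unexpected. But the protocol foresees sleep: as a possible mechanism (sections 1.2 and 10.1), through the driving restriction (section 6.2), and by allowing for children asleep at two hours (synopsis). Because section 11.1 limits adverse events to unfavourable and unintended signs, mild sleepiness may not be one at all. Some protocol text and the study manual are also not available to this review.
- *The ethics board trigger is therefore meaningless.* Section 16.2 does require the board to be told of "serious and/or unexpected adverse experiences occurring during the study", but the sentence goes on to defer to the board's own procedures, which are not in the documents.

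Nor can it be said that known reactions are graded Definitely whatever their timing, without qualification. The adverse event definition softens that, as set out in the working. The statement in section 9.1.6 that events may be reported at any time concerns reporting, not when the event occurred.

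**Conclusion.** Two drafting defects in Table 2 hold on its wording.

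1. A plausibly timed event of a new type, not certainly unrelated, has no grade. This holds under either reading of Definitely.
2. A previously known toxicity qualifies as Definitely without a reasonable-sequence test and even when another cause readily explains it. This rests on the plain reading, in which the known-toxicity alternative stands alone. The stricter reading shrinks it to 2 of 12 combinations but still admits one without a reasonable sequence.

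The counts describe logical cases, not expected event frequencies. The documents give no basis for saying how many events would be misgraded. The reach is the relationship column of the adverse event tables by dose group, a descriptor of tolerability. The primary VAS comparison is untouched. Serious adverse events are documented and reported whether or not related (sections 11.2.1 and 16.2), so that safeguard does not depend on the grade. The change is worth making because it is cheap and the rules are stated rules, not because a wrong dose choice has been shown.

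**What to change.** Reword three rows of Table 2:

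- **Possibly:** a reasonable temporal sequence where a relationship to the drug cannot be excluded, whether or not the pattern is known and whether or not other factors could explain the event, and the criteria for a higher grade are not met.
- **Unrelated:** no reasonable temporal sequence, or clearly explained by another cause.
- **Definitely, known-toxicity route:** add a reasonable temporal sequence and no other reasonable explanation.

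Three lighter edits would not be enough. Deleting only the pattern condition from Possibly leaves a well-timed new event ungraded when no alternative cause is readily available. Defining Unrelated as more likely due to another cause would overlap with Possibly. Adding only timing to the known-toxicity route would still give Definitely to an event that migraine readily explains.

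Naming a reference for expected reactions in section 11.1 would be a useful clarification, but it is optional and repairs neither defect.

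The cost is a text amendment with the usual ethics board approval. It needs no new data, visits or participants. The downside is that some events will move between Definitely, Possibly and Unrelated, so any events already graded should be regraded under the new text before the tables are produced.

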11.2 Serious Adverse Experiences (SAE)

An SAE is defined as any AE occurring at any dose that results in any of the following outcomes:

- death
- a life-threatening adverse experience
- inpatient hospitalization or prolongation of existing hospitalization

- a persistent or significant disability/incapacity
- a congenital anomaly/birth defect

Other important medical events may also be considered an SAE when, based on appropriate medical judgment, they jeopardize the subject or require intervention to prevent one of the outcomes listed.

11.2.1 Serious Adverse Experience Reporting

Study sites will document all SAEs that occur (whether or not related to study drug) per [UCSF CHR Guidelines](#). The collection period for all SAEs will begin after informed consent is obtained and end after procedures for the final study visit have been completed.

In accordance with the standard operating procedures and policies of the local Institutional Review Board (IRB)/Independent Ethics Committee (IEC), the site investigator will report SAEs to the IRB/IEC.

12 DISCONTINUATION AND REPLACEMENT OF SUBJECTS

12.1 Early Discontinuation of Study Drug

A subject may be discontinued from study treatment at any time if the subject, the subject's parent/guardian, or the investigator think that it is not in the subject's best interest to continue.

If a subject is withdrawn from treatment due to an adverse event, the subject will be followed and treated by the Investigator team until the abnormal parameter or symptom has resolved or stabilized.

All subjects who discontinue study treatment should tell the study site.

All subjects are free to withdraw from participation at any time, for any reason, specified or unspecified, and without prejudice.

12.3 Withdrawal of Subjects from the Study

A subject may be discontinued from study treatment at any time if the subject, the subject's parent/guardian, or the investigator think that it is not in the subject's best interest to continue.

All subjects are free to withdraw from participation at any time, for any reason, specified or unspecified, and without prejudice.

12.4 Replacement of Subjects

Subjects who withdraw from the study treatment will not be replaced.

Subjects who withdraw from the study will not be replaced.

13 PROTOCOL VIOLATIONS

A protocol violation occurs when the subject or investigator fails to adhere to significant protocol requirements affecting the inclusion, exclusion, subject safety and primary endpoint criteria.

Protocol violations for this study include, but are not limited to, the following:

Failure to meet inclusion/exclusion criteria

Use of a prohibited concomitant medication

Failure to comply with Good Clinical Practice (GCP) guidelines will also result in a protocol violation. The investigator will determine if a protocol violation will result in withdrawal of a subject.

When a protocol violation occurs, it will be discussed with the investigator and a Protocol Violation Form detailing the violation will be generated. This form will be signed by the Investigator. A copy of the form will be filed in the site's regulatory binder.

14 STATISTICAL METHODS AND CONSIDERATIONS

Prior to the analysis of the final study data, a Statistical Analysis Plan (SAP) will be written describing analyses that will be performed.

Data Sets Analyzed

All eligible patients who are randomized into the study and receive at least one dose of the study drug (the Safety Population) will be included in the safety analysis.

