6 SUBJECT SELECTION

6.1 Study Population

Subjects ages 3-17 inclusive with a diagnosis of episodic migraine who meet the inclusion and exclusion criteria will be eligible for participation in this study.

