9.1.7 Pregnancy Determination

During enrollment, female subjects who are of childbearing age will be asked if they could be pregnant.

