14.3 Analysis of Secondary Endpoints

Safety and tolerability data will be summarized by treatment group.

Adverse event rates will be coded by body system and MedDra classification term. Adverse events will be tabulated by treatment group and will include the number of patients for whom the event occurred, the rate of occurrence, and the severity and relationship to study drug.

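### The Safety Population is limited to eligible patients, so a dosed participant later found ineligible would be left out of the safety tables

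*Combined protocol and SAP*

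**What the plan says.** Under Data Sets Analyzed, section 14 takes "All eligible patients who are randomized into the study and receive at least one dose of the study drug (the Safety Population") and states that they "will be included in the safety analysis". Three conditions therefore apply jointly: eligible, randomized, and dosed at least once. No other analysis set is defined.

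Section 6.1 gives eligibility its meaning: subjects with episodic migraine in the stated age range "who meet the inclusion and exclusion criteria will be eligible for participation in this study". Section 13 includes "Failure to meet inclusion/exclusion criteria" among the protocol violations and adds that "The investigator will determine if a protocol violation will result in withdrawal of a subject". It does not say whether the data of such a subject stay in the safety analysis.

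Section 14.3 states that "Adverse events will be tabulated by treatment group and will include the number of patients for whom the event occurred". It names no population wider than the one in section 14. Section 14 also says that an SAP will be written before the final data are analysed.

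**The concern.** A safety analysis describes what happened to the people who took the product. Whether a participant met every entry criterion does not change the fact of exposure. A condition on eligibility can remove an exposed person for a reason unrelated to exposure, and after the outcome is known.

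Tolerability of the high against the low dose, overall and by weight stratum, is a secondary objective and endpoint (sections 3.2 and 5.2). It also has a decision role. Under section 2 and the synopsis (Study Design), if the doses are equally effective, tolerability decides which one goes into the later placebo-controlled study. With 19 participants planned per arm, one person in or out is visible in the tables.

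**Working it through.** The plan states no figure on this point, so there is none to reproduce. The check is mainly textual, followed by an illustration of size.

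**Reading the sections together**

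1. Entry to the safety set requires eligibility (section 14).
2. Eligibility means meeting the inclusion and exclusion criteria (section 6.1).
3. Enrolled subjects who do not meet them are foreseen (section 13).
4. Ineligibility could come to light after dosing. Pregnancy is an exclusion (section 6.3), but section 9.1.7 says only that "female subjects who are of childbearing age will be asked if they could be pregnant" and describes no test. Section 10.1 allows baseline data to be collected by phone for remote enrolment.
5. Nothing in sections 13, 14 or 14.3 brings such a participant back into the safety analysis.

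It follows that a dosed participant later found ineligible is outside the Safety Population as defined.

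**What is not affected**

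- Adverse events are recorded in the diary and CRF (sections 9.1.6 and 11.1) with no eligibility condition.
- For serious events, section 11.2.1 says "Study sites will document all SAEs that occur (whether or not related to study drug"), and section 16.2 has them reported to the IRB regardless of causality.
- The gap therefore concerns the analysis tables only.

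**Size of one omission**

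Input from the plan: 19 per arm (section 14.5), so 2 × 19 = 38 per dose group across the two weight strata. Assumptions: all 38 are dosed, and 4 have a given event. In a single stratum of 19, I assume 2 have it.

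| Setting | All exposed | One with the event left out | One without the event left out |
|---|---|---|---|
| Dose group of 38 | 4/38 = 10.5% | 3/37 = 8.1% | 4/37 = 10.8% |
| Stratum arm of 19 | 2/19 = 10.5% | 1/18 = 5.6% | 2/18 = 11.1% |

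One omission moves the dose-group rate down by 2.4 points or up by 0.3. In a single stratum arm it moves it down by about 5 points or up by 0.6. The synopsis also gives a total of 100 subjects. With 50 per group and the same 4 events, 4/50 = 8.0% becomes 3/49 = 6.1% or 4/49 = 8.2%.

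**Chance that an event is missed**

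Let k be the number dosed but ineligible and a the proportion of participants with an adverse event. The documents give neither. If events are independent of eligibility, the chance that at least one participant with an event is left out is 1 − (1 − a)^k. The assumed range is 1% to 10% of 76 participants, so k runs from 1 to 8, with a from 5% to 30%:

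- k = 1, a = 5%: 1 − 0.95 = 5%
- k = 2, a = 10%: 1 − 0.90² = 19%
- k = 8, a = 30%: 1 − 0.70⁸ = 94%

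The upper end needs many ineligible participants, which nothing in the documents suggests.

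**The case against.** The sponsor could reply that *eligible* was meant loosely, as enrolled. No removal procedure is described, and the detail is left to an SAP still to be written. The violation list also looks generic: it names use of a prohibited medication, although the synopsis prohibits none. Migraine criteria are verified before enrolment (section 10.1) and there are only three exclusions (section 6.3), so cases should be rare.

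The argument about rarity stands, and it limits the impact. The loose reading does not, because section 6.1 defines the term by the criteria and no section says otherwise. If enrolled was the intended meaning, deleting the word loses nothing.

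A reader might go further in three ways that the documents do not support:

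- *Adverse event rates are biased downward.* The direction depends on who is left out, as the table shows. Ineligibility that was present before randomization should also be balanced between doses in expectation. Tipping the dose choice would need chance imbalance, or discovery of ineligibility prompted by an event, and neither is shown.
- *Those left out are the ones most likely to have an informative event.* This looks only at the exclusions, such as allergy or intolerance. Failing an inclusion criterion in section 6.2, such as attack frequency, also makes a participant ineligible and has no evident link to adverse events. Nothing in the protocol says that a first reaction to the product during the study makes a participant ineligible in retrospect.
- *Safety information is lost altogether.* Collection of adverse events and reporting of serious ones carry no eligibility condition.

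**Conclusion.** The definition is wrong as written, with minor impact. On its plain wording, section 14 leaves dosed but ineligible participants out of the safety analysis, and no other section restores them. This is a stated rule that gives the wrong set, rather than missing detail.

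Confidence is high on the wording and low on any numerical effect. The number of such participants is not given and is probably small. The rates shown rest on assumed event counts and on everyone randomized being dosed. Tolerability decides between the doses only if they are judged equally effective, so an effect on the dose choice is possible but not demonstrated. The point is worth correcting because the safety set should not depend on a later judgement about eligibility, and the correction is easy.

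**What to change.** In section 14, delete *eligible*. The Safety Population then consists of all randomized participants who receive at least one dose of study drug, regardless of any ineligibility discovered later. Keep the tabulation by treatment group as in section 14.3. Carry the same definition into the SAP, with a sentence saying that a protocol violation or withdrawal under section 13 does not remove a dosed participant from this set.

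The cost is one deleted word in the protocol and one sentence in the SAP, submitted to the IRB as an amendment under section 16.1. No additional data are needed, and sample size and conduct do not change.
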